- Does the need for close integration with other health care providers, e.g. primary care, impact the feasibility and costs associated with delivering the new care model?

Quantitative evaluation - general principles

A range of quantitative data (clinical, process-driven and economic) will be collected and analysed as part of a mixed methods evaluation in this project. However, definitive evaluation of the impact of group clinics is not possible within this study for several reasons. First, the intervention is not yet sufficiently developed; the intervention will be codesigned at the beginning of the study period; it will then be refined and improved throughout the remainder of the study period. Second, the timescale of our study is not long enough to evaluate the full impact of new behaviours such as increased exercise, diet changes, clinic attendance. Third, our study focuses on in-depth analysis of a relatively small group of patients, so is not powered to detect a small/moderate effect of group clinics. For example, to show a statistically significant improvement in HbA1c results in the 214 patients attending the young adult clinic, the average HbA1c result would have to decrease from 68 to 57mmol/l for people with Type 2 diabetes, and 86 to 79mmol/l for those with Type 1 diabetes; we do not think is a realistic goal within the timeframe of this project. Lastly, there is uncertainty about the most appropriate outcome measures with which to evaluate impact (i.e. we do not know whether traditionally-used outcome measures for diabetes studies will be the most relevant for these populations and for the anticipated effects of this intervention).

With these limitations in mind, the quantitative analysis will instead focus on:

- Detailed, descriptive comparisons of clinical and service-based outcomes in Newham before/after the introduction of group clinics for young adults.
- Comparison of clinical and service-based outcomes (i) at unit level, between comparable services at Newham University Hospital, the Royal London Hospital and the Whittington Hospital, and (ii) at national level, using National Diabetes Audit data to understand heterogeneity and generalisability.
- Assessing the feasibility of collecting clinical, process and cost data at patient- and unit-level to enable the design of a future cluster randomised controlled trial.

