Data collection: the principle clinical outcome measures will reflect:

- Biological markers of diabetes control and complications: we will use markers of control and complications that are also benchmarked as key care processes in the National Diabetes Audit (run by the HSCIC). These are: HbA1C (a measure of glycaemia), blood pressure, serum cholesterol, creatinine, albuminuria, foot surveillance, body mass index, smoking. We will also analyse data on retinal screening if this is included in future national audits. These data will also be collected from, (a) individuals recruited as 'control data participants' (n=60) at external units running young adult diabetes clinics, at the Whittington Hospital NHS Trust, and Barts Health NHS Trust (including Royal London, Mile End, Barts and Whipps Cross Hospitals), and (b) national level data from the HSCIC National Diabetes Audit in an age-matched group.
- Routinely-collected data on outpatient hospital activity: The principal measure for both will be Did Not Attend (DNA) rates in outpatient clinic. (currently 28% at Newham University Hospital). It is important to note that attendance at consultant-led, hospital clinics is often seen as a key measure of patient engagement, but its role in evaluating group clinic deserves further investigation. It may be that attendance at group clinics is perceived by both patients and professionals as a reason to decrease the frequency of clinic attendance. So the quantitative analysis of DNA rates for hospital clinics must be interpreted alongside attendance rates at group clinics and the qualitative findings about the optimal role of group clinics for different patients. Another caveat is that the relationship between DNA rates and clinical outcomes may vary when the frequency of hospital clinic appointment visits changes, e.g. reduce from 6 monthly clinics to annual review. As noted above, preliminary quantitative findings will be discussed and the value of each measure will be explored by the qualitative research team in their evaluation. These data will also be collected for unit-level comparison from the young adult diabetes clinics at the Whittington Hospital NHS Trust, and Barts Health NHS Trust (including Royal London, Mile End, Barts and Whipps Cross Hospitals).
- Indirect markers of clinical outcome: data on unplanned hospital admissions and GP attendance frequency related to diabetes in the target group will be collected as part of a costing analysis of resource use.

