- Comparison to external individual (control data participants) and unit-level data using clinical outcome (and indirect clinical outcome) data collected from young adult diabetes clinics at the Whittington Hospital NHS Trust and Royal London Hospitals. This data analysis will inform a future scaled-up cluster-randomised controlled trial of group clinics by (i) testing the feasibility of unit-level data collection, (ii) identifying differences in the case mix of patients attending young adult diabetes clinics, (iii) characterising the clinical and process outcomes of young adults with diabetes under the care of different units.
- Comparison to national clinical outcome and process benchmark data in an age-matched population from the National Diabetes Audit.

(iii) Costs analysis

We will apply national unit costs to all resource use to estimate relevant staffing capital and running costs related to running the standard vs. group clinics at Newham University Hospital. We will then fully describe resource inputs and costs associated with delivering group clinics (e.g. venue, consultancy and staffing costs) and the impact on use and costs of other core services. Data will be presented in both aggregated and disaggregated form, and for different scenarios e.g. group clinic costs according to variations in attendance rates. Using the comparative approach described above for each patient group, we will assess the impact on use of other services and associated costs, and thus the extent to which the group clinic model substitutes for, rather than adds to, standard care. This in turn will provide an early indication of any potential for efficiency savings for the NHS.

Delivery

Qualitative and quantitative evaluation and analysis of costs will be performed by a research team, independent and external to the implementation team, which includes specific expertise in quantitative evaluation of clinical and economic outcomes in diabetes trials, as well as broad experience evaluating studies into other long-term conditions and the health economic impact of new models of care. The research team will also be supported by the Institute of Child Health Statistical Support Service, who will advise on, and quality assure all stages of the quantitative evaluation including study design, analysis and use of study data to inform a future cluster-randomised controlled trial.

Anticipated outputs

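### The national audit benchmark is matched on age alone and the external-unit comparison states no matching, although the protocol's own HbA1c averages differ by 18 units between Type 1 and Type 2

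*Protocol*

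**What the plan says.** The national comparator is defined twice in Workstream 4 (ii), both times by age alone. Under Data collection it is "national level data from the HSCIC National Diabetes Audit in an age-matched group". Under Data analysis the plan lists a "Comparison to national clinical outcome and process benchmark data in an age-matched population from the National Diabetes Audit".

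The comparison with the Whittington and Royal London clinics, under the same Data analysis heading, names no matching variable. One of its three listed purposes is "identifying differences in the case mix of patients attending young adult diabetes clinics". Nothing says how those differences will be carried into the comparison of outcomes.

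Under Quantitative evaluation - general principles, the protocol gives HbA1c by type. Its example concerns a clinic of 214 patients. For significance there, it states that "the average HbA1c result would have to decrease from 68 to 57mmol/l for people with Type 2 diabetes". The corresponding fall in Type 1 is given as one from 86 to 79. The authors do not expect changes of this size and write of them: "we do not think is a realistic goal within the timeframe of this project".

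Two other places bear on the point:

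- Workstream 1 (iii), Formative evaluation, lists the numbers of patients with Type 1 and Type 2 diabetes among the items to be mapped, and says the exercise will take place at three units.
- The list of markers for control data participants in Workstream 4 does not name diabetes type. It also allows recruitment at Barts Health hospitals outside those three units.

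**The concern.** The two types differ widely in average HbA1c in the protocol's own clinic. If Newham and a comparator hold the types in different proportions, their pooled averages differ for that reason alone, and matching on age does not remove it. A service with more Type 2 patients would look better controlled, and one with more Type 1 patients worse, whatever the quality of care.

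This matters because the benchmark has a stated use. The opening summary of Workstream 4 says that audit comparison and benchmarking against other centres will indicate whether group clinics could improve clinical outcomes. The operational objectives include comparing Newham's processes, outcomes and costs with the audit and the two local services. The unit-level and national data are also meant to guide sample size and the choice of endpoints for a later cluster-randomised trial. Differences between clinics that are really differences in type mix would pass into that design as heterogeneity of care.

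**Working it through.** **Inputs from the protocol** (Quantitative evaluation - general principles, and Workstream 4): average HbA1c 86 for Type 1 and 68 for Type 2; falls needed for significance, 86 − 79 = 7 and 68 − 57 = 11; clinic size 214, with no split by type; 80 to 100 group clinic participants and 60 control data participants. The protocol prints the HbA1c unit as mmol/l; the arithmetic does not depend on it.

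**The protocol's own figures.** The falls of 7 and 11 cannot be reproduced, because the standard deviation, power, significance level, type split and test are not given. They can be checked for plausibility. Assume equal standard deviations in the two types, independent groups, two-sided 5% and 80% power. The detectable difference is then proportional to 1/√n, so n₁/n₂ = (11/7)² = 2.47, which puts about 71% of the clinic, or 152 of 214, in Type 1. The standard deviation is 7 / (2.80 × √(2/152)) = 21.8. The figures are plausible but not verifiable, and the 71% is an inference from assumptions, not a stated mix.

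**Shift from type mix.** With Type 1 share p, the pooled mean is 86p + 68(1 − p) = 68 + 18p. If the type-specific means are the same at both sites, the pooled difference is 18 × (difference in p).

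| Difference in Type 1 share (assumed) | Shift in pooled HbA1c |
|---|---|
| 10 points | 1.8 |
| 20 points | 3.6 |
| 30 points | 5.4 |
| 40 points | 7.2 |

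**Share difference that equals a given effect, E/18.** For the protocol's figures: 7 needs 7/18 = 38.9 points, and 11 needs 11/18 = 61.1 points. For smaller effects, which are assumed: 2 needs 11.1 points, 3 needs 16.7, 4 needs 22.2 and 5 needs 27.8.

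**Chance imbalance.** Take 90 group clinic participants (the middle of 80 to 100) and 60 controls from populations with the same mix, with Type 1 share assumed to be 50% to 70%. The 95% range of the share difference is ±1.96 × √(p(1 − p)(1/90 + 1/60)). At p = 0.5 this is ±16.3 points, or ±2.9 units of HbA1c. At p = 0.7 it is ±15.0 points, or ±2.7 units.

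**Effect of the fix, on an assumed example.** Let Newham be 60% Type 1 and a comparator 80%, with type-specific means of 86 and 68 at both. The pooled means are 68 + 18 × 0.6 = 78.8 and 68 + 18 × 0.8 = 82.4, a difference of 3.6. Within each type the difference is 0. Standardising the comparator to Newham's 60% also gives 78.8 and a difference of 0.

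**The case against.** The strongest reply is that the quantitative work is openly descriptive. The protocol says that definitive evaluation is not possible in this study and that the unit and national comparisons serve to understand heterogeneity and generalisability. It never says that outcomes will be pooled across types, its only HbA1c figures are split by type, and type counts are to be collected. Stratification could be set out in an analysis plan that is not shown, and a statistical support service is to advise on analysis.

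Much of this is fair, and it limits the weight of the point. It does not remove it. The protocol does not leave the matching open: it names age, twice, including in the text on which data will be obtained. If audit figures arrive as an age-matched aggregate, no later plan can split them. A descriptive comparison that mixes care with case mix is still hard to read.

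Stronger readings are tempting but not supported:

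- A reader might infer that type mix could swamp any effect. It takes a difference of 39 or 61 points in Type 1 share to equal the protocol's 7 or 11, and no site's mix is given.
- A reader might take the external-unit comparison to be matched on age only. No matching at all is stated for it, and describing case mix is one of its aims.
- A reader might extend the concern to the difference-in-difference analysis and ask for type as a covariate. That analysis compares people who accept group clinics with people who decline. A person's type is fixed, so the 18-unit gap in level cancels in the change from baseline. Only different trends by type would matter, and the documents give nothing on those.

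**Conclusion.** The point holds for comparisons of HbA1c level with the audit and the external units. Followed as written, an age-matched pooled benchmark is confounded by diabetes type at 1.8 units per 10-point difference in Type 1 share. This rate assumes that the 18-unit gap seen at Newham applies at the comparators.

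The actual bias cannot be stated, because it depends on a type mix that the documents do not give. At an assumed 10 to 20 points it would be 1.8 to 3.6 units. That is well short of the falls of 7 and 11, but the protocol itself regards those as unrealistic in its timeframe, so the effects it might plausibly see are smaller and a shift of this size could be mistaken for one. For the 60 external controls, chance alone could produce nearly 3 units.

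The gap is shown only for HbA1c. The documents give no figures by type for care processes or missed appointments, so the conclusion does not extend to them. Given the developmental purpose, this is a worthwhile correction to the specification and does not undermine the study.

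**What to change.** In Workstream 4 (ii):

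1. Change the audit comparator, under both Data collection and Data analysis, from age-matched to matched or stratified by age and diabetes type, and request the audit data by type.
2. Record diabetes type for each control data participant. The unit counts from the formative evaluation are not enough, since they are not tied to individuals and cover only three units.
3. Report HbA1c level comparisons with the audit and the external units within Type 1 and within Type 2, or standardised to Newham's type mix.
4. Show the type mix of each group next to every such comparison.

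The cost is small but not nil. The audit extract must be more detailed, and the documents do not say whether one by age and type is available. Splitting 60 external controls by type leaves small cells and wider intervals; where a cell is too small to report alone, the standardised figure can be shown with that limitation stated.

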- health advocates will facilitate participation of patients where a language barrier exists, and we will monitor progress and barriers. Although our study will not include any participants under the age of 16, particular attention will also be paid to the needs of those aged 16-18, and those with learning disabilities or other relevant needs.
- Informed consent will be secured in order to access routinely collected NHS data on participants. Subject to approval by the ethics committee, we will also ask participants to consent to long term follow up and appropriate linkage of their data.
- All staff members will have up-to-date Good Clinical Practice qualifications.
- Information governance procedures will be followed and regular data and process audits will take place.

Patient and Public Involvement

Patient and Public Involvement (PPI) is central to the development of this project and for the plans on how it will be executed. PPI has already directly informed the development of the initial idea and will be critical to the design of the group clinics, and the patient community will be closely involved with the project's evaluation. Patients and the local public will also be central to dissemination activities. Proposed PPI activities will strengthen the relevance, accessibility and success of the project.

The **initial proposal and project design** were informed by patients and the public in the following ways:

- A 1-year pilot project was undertaken in Newham exploring scope and feasibility of peer-support groups to
 improve patient engagement and self-management for young people 16-25 years with diabetes. This led to
 suggestions from patients that health and social care needs should be integrated, and that projects should include
 age appropriate content, multi-agency work and increased use of social networks.
- Women receiving antenatal diabetes care at Newham recently completed a peer-support diabetes education programme and identified a clear challenge in accessing structured diabetes care.
- The Association for Young People's Health has an active youth participation strand that has provided messages about the positive contribution of groups in promoting health in vulnerable groups, and collaboration with a young adult living with diabetes has provided expert patient input.
- In the planning stages a lay summary of the proposal was drawn up & shared with (a) a group of 6 young people (aged 15-24) from the Royal College of Paediatrics and Child Health's Youth Advisory Panel, and (b) a focus group of women with diabetes in the antenatal clinic at Newham Hospital. Feedback from both groups was extremely useful and fed directly into the research design

As the project unfolds, patients and other local community members will be actively engaged in the following ways:

- The project will use the Experience Based Co-Design Toolkit, adapted for our specific patient groups and their sensitivities, as a basis for designing the content of the group clinics and ideas about how they will work in practice. This work will be led by the Association for Young People's Health.
- Young adults with diabetes will be supported as members of the project advisory group and other project
 management groups, or alternative ways of getting their input to these groups will be designed with them, as
 appropriate.
- There will be ongoing collaboration with the Newham CCG Youth Champion who will work closely with the research team, and be involved in facilitating the local user-group.
- The Researcher in Residence model will enable us to communicate with patients informally as well as formally as the project develops, as the researcher will be visible and available on the premises
- We will engage wider canvassing of PPI input on the findings, using SurveyMonkey & social media (e.g. Twitter), pulling in a broader group than the patients and local stakeholders directly involved, for discussion and validation of main messages.
- Working with patients, we will prepare lay versions of research outputs for PPI and stakeholder audiences, including a practitioner & policy brief.
- Links have already been made with local PPI experts such as Newham CCG's PPI Officer, with whom we will work collaboratively again to ensure a wider group is reached.
- A final PPI event is proposed, reflecting on messages and their implications.

Expertise and justification of support required

